10.16. Local vendor documentation

This study requires a vendor. Appropriate certifications and documentation records are required to be maintained at the site for vendor.

11. Statistical Considerations

11.1. *Endpoints*

11.1.1. *Primary Endpoints*

11.1.1.1. *Primary Safety Endpoint*

The primary safety endpoint at 30 days consists of acute primary safety endpoint events as defined in **Section 6**, which will be assessed after all the enrolled subjects finishing One-month Visit data collection.

11.1.1.1.1 *Hypothesis*

This is an observational real-world study with small sample size, no formal hypothesis is performed in this study.

11.1.1.1.2 *Sample Size*

There is no formal hypothesis for this study, thus no sample size calculation is performed in this study. The study device has achieved CE mark and accumulated a large amount of clinical data. This trial with 30 PAF subjects will be used to produce data in Chinese population.

The following table provides a 95% confidence interval (exact methods) for a sample size of 30 if there are 0 ~ 3 primary safety events.

Safety Events	Rates (n=30)	Lower 95%CI	Upper 95%CI
0	0%	0%	11.6%
1	3.3%	0.1%	17.2%
2	6.7%	0.8%	22.1%
3	10%	2.1%	26.5%

11.1.1.1.3 *Statistical Methods*

Descriptive statistics will be conducted for the safety endpoint events. The number, incidence (amount of events/number of subjects) and its 95% confidence interval (exact methods) will be calculated. The primary safety endpoints will be analyzed for ATTEMPT and TREATMENT subjects in the ITT set. Explorative statistical analysis might be produced if appropriate, e.g., Bayesian estimation of the study results using FARAPULSE IDE data as the prior.

11.1.1.2. *Primary Effectiveness Endpoint*

The primary effectiveness endpoint is the acute procedural success, defined as proportion of subjects that achieved PVI with FARAPULSE Pulsed Filed Ablation system only, which will be assessed after all the enrolled subjects finishing One-month Visit data collection.

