5.4.2. Anticoagulation

5.4.2.1. Pre-ablation

Physicians is highly recommended to follow guidelines or expert consensus statements for the management of Patients with AF for adequate systemic anticoagulation. For patients with anticoagulation therapy before the procedure, an uninterrupted anticoagulation approach is recommended.

5.4.2.2. *Intra ablation*

Physicians is highly recommended to follow guidelines or expert consensus statements for the management of Patients with AF and FARAPULSE Pulsed Field Ablation IFUs for adequate anticoagulation during procedure. It is recommended that heparin be administered prior to or immediately following transseptal puncture or use of the mapping catheter (if available) during AF ablation procedures and the heparin is adjusted to achieve and maintain an ACT of at least 300 seconds. A procedural ACT between 300 seconds and 450 seconds should be maintained until all devices are withdrawn from the left atrium.

5.4.2.3. *After ablation*

Adherence to AF anticoagulation guidelines is recommended for subjects who have undergone an AF ablation procedure, regardless of the apparent success or failure of the procedure. Warfarin or NOAC anticoagulation is recommended for using for at least 2 months after ablation. Whether to continue anticoagulation after 2 months is determined by the clinician based on the patient's condition.

6. Study Objectives and Endpoints

6.1. *Study Objectives*

The objective of the study is to observe the safety and effectiveness of the FARAPULSE Pulsed Field Ablation system for treatment of recurrent, symptomatic PAF in a Chinese population in the real world. The overview of primary and secondary objectives and endpoints are summarized in **Table 6.1-1**.

Table 6.1-1: Overview of Primary and Secondary Objectives and Endpoints

OBJECTIVES	ENDPOINTS	JUSTIFICATION FOR ENDPOINTS
Primary Endpoints		
Observe the acute safety of the FARAPULSE Pulsed Field Ablation system	The primary safety endpoint is defined as occurrence of the acute serious procedure-related and/or device-related adverse events at 7 days post index procedure. Primary safety events will consist of a composite of serious procedure and/or device-related adverse events.	The list of events contributing to the primary safety endpoints was selected from those typically associated with catheter ablation of AF.

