11.1.2. Secondary Endpoints

11.1.2.1. Secondary Safety Endpoints

The secondary safety endpoint will evaluate the proportion of subjects that free from primary safety events defined in **Section 6** through 7 days after the procedure and free from the following serious procedure-related and/or device-related adverse events at any time through the completion of 12-month follow-up visit, which will be assessed at the time of the twelve-month analysis:

- Atrial esophageal fistula
- Severe PV stenosis
- Persistent phrenic nerve palsy*

**The study will collect information on phrenic nerve palsy observed before the end of the index procedure and, in case of occurrence, will track information for potential recovery during the study visits.*

11.1.2.2. Secondary Effectiveness Endpoint 1

The first secondary effectiveness endpoint will evaluate the chronic success, which is defined as proportion of subjects that free from effectiveness events defined as failure as below at twelve months post-procedure.

Effectiveness events determining a failure are defined as:

- Fail to achieve electrical isolation of all PVs using FARAPULSE Pulsed Filed Ablation system only.
- After the Blanking Period to 12-month after the procedure:

- a) Occurrence of any Detectable AF, AFL* or AT captured by one of the following methods: ≥ 30 seconds in duration recording from 24-hour or longer Holter Monitor or ≥ 10 seconds recording from 12-lead ECG.
- b) Any cardioversion for AF, AFL* or AT.
- c) Use of any Class I or Class III AADs[#] for the treatment of AF, AFL* or AT.
- At any time through 12 months after the procedure:
 - a) Re-ablation for AF, AFL* or AT.
 - b) Use of amiodarone, except intra-procedurally to control an arrhythmia.

#It won't be considered as a failure if the subject has three-month visit happened after 90 days post the procedure, but still in the window (≤ 104 day) with AADs on, and physicians decide to take AADs off after this visit.

**excluding CTI-dependent flutter confirmed by EP study*

11.1.2.3. Secondary Effectiveness Endpoint 2

The second secondary effectiveness endpoint will evaluate the proportion of PVs that achieve electrical isolation by using the FARAPULSE Pulsed Field Ablation system only.

11.1.2.4. Secondary Effectiveness Endpoint 3

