11.2. General Statistical Methods

Descriptive statistics will be conducted for the primary, secondary and other endpoint events. When descriptive statistics are used, continuous variables will be summarized using standard quantitative statistics: number of available observations, mean, standard deviation, median, quartiles and range (minimum and maximum observed values) and its 95% confidence interval. Categorical variables will be summarized using the number, incidence (amount of events/number of subjects) and its 95% confidence interval (exact methods).

Explorative statistical analysis might be produced if appropriate, e.g., Bayesian estimation of the study results using FARAPULSE IDE data as the prior.

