11.3.1. Primary Endpoints/Measurements

The primary safety and effectiveness endpoints will be analyzed after all the enrolled subjects finishing One-month Visit data collection. The primary safety endpoint will be analyzed for ATTEMPT and TREATMENT subjects in ITT set. The primary effectiveness endpoint will be analyzed for TREATMENT subjects in mITT set. Descriptive statistics will be conducted for the effectiveness endpoint events. The number, incidence (amount of events/number of subjects) and its 95% confidence interval will be calculated (exact methods). Explorative statistical analysis might be produced if appropriate, e.g., Bayesian estimation of the study results using FARAPULSE IDE data as the prior.

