18.1. Reportable Events by investigational site to Boston Scientific

It is the responsibility of the investigator to assess and report to BSC any event which occurs in any of following categories:

- All adverse events
- All serious adverse events
- All Adverse Events related to FARAPULSE Pulsed Field Ablation system
- All Serious Adverse Events related to FARAPULSE Pulsed Field Ablation system
- All Adverse Events related to the Procedure
- All Serious Adverse Events related to the Procedure
- All Device Deficiencies
- Unanticipated Adverse Device Effects/Unanticipated Serious Adverse Device Effects
- New findings/updates in relation to already reported events

When possible, the medical diagnosis should be reported as the Event Term instead of individual symptoms.

If it is unclear whether or not an event fits one of the above categories, or if the event cannot be isolated from the device or procedure, it should be submitted as an adverse event and/or device deficiency

The following clinical events will not be considered adverse events for this clinical study:

- Pre-existing diseases or conditions (including AF, AFL, AT) will not be reported as adverse events unless there has been a substantial increase in severity or frequency of

the problem as compared to the subject's baseline which cannot be attributed to the expected progression of the disease or condition.

- Pre-planned hospitalizations before the index procedure or for a pre-existing condition.
- AF/AFL/AT episodes with medical intervention or hospitalization due to arrhythmia recurrence during the blanking period.
- If an additional ablation procedure is required, this additional ablation procedure should only be considered an AE if it is associated with subject worsening condition or a new diagnosis. The ablation would be considered a corrective action.

If the subject experiences a new or worsening arrhythmia between the index procedure and the end of study, and the investigator considers this AE to be study related, it needs to be reported. Refer to Investigator's Brochure or IFU as appropriate for the known risks associated with the study device(s).

Any reportable event, experienced by the study subject after informed consent, whether prior to, during or subsequent to the procedure, must be recorded in the eCRF.

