Prolongation of hospitalization	
In-patient admission to the hospital that is prolonged beyond the expected standard duration for the condition under treatment.
 
Note: new adverse events occurring during the hospitalization are evaluated to determine if they prolonged hospitalization or meet another SAE criterion.

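### The incidence rule for the composite primary safety endpoint has no count-once provision: read literally, it counts a subject with two qualifying events twice (minor correction)

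*Protocol*

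**What the plan says.** Protocol Table 6.1-1 defines the primary safety endpoint as the occurrence of listed events at 7 days and adds: "Primary safety events will consist of a composite of serious procedure and/or device-related adverse events". Protocol 6.2.1.2 lists 13 components.

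The analysis rule in Protocol 11.1.1.1.3 is: "The number, incidence (amount of events/number of subjects) and its 95% confidence interval (exact methods) will be calculated". Protocol 11.2 extends it to every categorical variable, Protocol 11.3.1 repeats it for the primary endpoints, and SAP 3.2.3 and SAP 4 carry the same words. The planning table in Protocol 11.1.1.1.2 is also indexed by events: it gives exact intervals "for a sample size of 30 if there are 0 ~ 3 primary safety events".

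The secondary safety endpoint in Protocol 11.1.2.1 is counted differently: "The secondary safety endpoint will evaluate the proportion of subjects that free from primary safety events defined in" Section 6, and free from three later events.

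Two provisions of Protocol 18 bear on how events are recorded. Section 18.1 says: "When possible, the medical diagnosis should be reported as the Event Term instead of individual symptoms". A note in Table 18.2-1, under prolongation of hospitalization, says: "new adverse events occurring during the hospitalization are evaluated to determine if they prolonged hospitalization or meet another SAE criterion".

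For the lesser point, Protocol 11.1.2.3 defines the second secondary effectiveness endpoint as a proportion of veins. Protocol 11.3.2 nevertheless gives the secondary effectiveness endpoints, without exception, the rule of events over subjects with an exact interval.

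**The concern.** An exact binomial interval describes n subjects who each contribute 0 or 1. A count of events divided by subjects meets that condition only if no subject has more than one event. With 13 components, nothing in the text guarantees this. A subject could, for example, have a tamponade and a separate access-site complication in the same week.

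The study has no hypothesis test, so the estimate and its interval are the result. If events are counted, the error runs in one direction: the subject-level risk is overstated. One report could also show 2/30 with a primary safety event beside 29/30 free from those events, with no rule in the plan to reconcile them.

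For the vein endpoint, events over subjects is not a proportion at all. An exact interval on veins would treat veins of the same subject as independent.

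**Working it through.** **1. The plan's own table.** Two-sided Clopper-Pearson for x out of n: lower limit = 2.5% quantile of Beta(x, n-x+1); upper limit = 97.5% quantile of Beta(x+1, n-x). With n = 30:

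| x | x/30 | Recomputed 95% CI | Printed (Protocol 11.1.1.1.2) |
|---|---|---|---|
| 0 | 0% | 0-11.57% | 0-11.6% |
| 1 | 3.33% | 0.08-17.22% | 0.1-17.2% |
| 2 | 6.67% | 0.82-22.07% | 0.8-22.1% |
| 3 | 10.0% | 2.11-26.53% | 2.1-26.5% |

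Every row reproduces. These are intervals for x *subjects* out of 30, so the table already presumes the numerator that the text does not state.

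**2. One subject with two qualifying events (assumed example), no other subject affected.**
- Counting subjects: 1/30 = 3.3% (0.1-17.2%).
- Counting events: 2/30 = 6.7% (0.8-22.1%).
- Secondary safety endpoint, if nothing further happens: 29/30 free from events.

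**3. How likely this is.** Let p be the chance that a subject has a primary safety event, and q the share of affected subjects with a second one. The chance of at least one double count in 30 subjects is 1 - (1 - pq)^30. For p, Protocol 4.1.3 gives 1/81 (1.2%) and 2/71 (2.8%), both at 30 days; the 7-day figure of 1/40 (2.5%) lies between them. I treat these as subject-level rates. The expected number of affected subjects is 30 x 1/81 = 0.37 to 30 x 2/71 = 0.85. The documents give no value for q, so it is an assumption:

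| q (assumed) | p = 1/81 | p = 2/71 |
|---|---|---|
| 2% | 0.7% | 1.7% |
| 5% | 1.8% | 4.1% |
| 10% | 3.6% | 8.1% |
| 20% | 7.1% | 15.6% |

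**4. Vein endpoint.** Assume 30 subjects with four veins each. If all are isolated, events over subjects is 120/30 = 4.0, which is not a proportion. With veins as denominator, 120/120 gives 97.0-100%, whereas 30/30 subjects gives a lower limit of 88.4%.

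For an assumed 116/120 (96.7%), the effect of clustering can be gauged by dividing the 120 veins by a design effect: the between-subject variance of the mean over p(1-p)/120, held between 1 and 4.

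| Where the four failures fall | Design effect | Effective n | 95% CI |
|---|---|---|---|
| Ignored (plain exact) | - | 120 | 91.7-99.1% |
| Four subjects, one each | 0.93, set to 1 | 120 | 91.7-99.1% |
| Two subjects, two each | 2.00 | 60.1 | 88.5-99.6% |
| All in one subject | 4.14, set to 4 | 30 | 82.8-99.9% |

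In a beta-binomial simulation (40,000 runs, assumed within-subject correlations of 0.1 to 0.5), the plain interval covered 0.811 to 0.939 of the time at 95% isolation, and 0.933 to 0.981 at 97-99%. The adjusted interval covered 0.927 to 0.962 and 0.986 to 0.992 respectively. Near complete isolation the plain interval does little harm, and this particular adjustment is conservative.

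**The case against.** The strongest reply is that subjects were plainly meant. The same formula is attached to acute success (Protocol 11.1.1.2.3, SAP 3.1.3) and, through Protocol 11.3.2, to chronic success. Both are proportions of subjects, so an event there can only be a subject with the outcome. The safety endpoint is worded as an occurrence, exact methods presuppose a binomial count, and the planning table is an ordinary binomial table. This stands as evidence of intent. It does not supply the missing rule, and a programmer who follows the formula for a 13-part composite could still count events.

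Several stronger readings are tempting, and the documents do not support them:

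- *That the plan commits to counting events, or permits double counting.* A reader might infer this from the note in Table 18.2-1. That note decides whether an adverse event is serious; it does not say how a composite numerator is formed.
- *That one effusion would count as both tamponade and pericarditis because the definitions overlap.* Protocol 18.1 asks for the diagnosis as the event term where possible, so one effusion would normally be one event.
- *That death would always add a second count.* Protocol 18.1 records death only as the outcome of one serious event, although Table 6.2-1 lists it as a component. The text does not settle the matter, and a count-once rule makes it irrelevant.
- *That the problem is likely.* The upper figures in the table above depend on shares with no source. Protocol 4.1.3 reports three named events in 121 subjects and mentions no subject with two.
- *That SAP 7.3 imposes a patient denominator on the vein endpoint.* That rule opens with baseline categorical variables and deals with missing values and visit completion.
- *That one particular clustering method is required.* Several are acceptable, and the one used above over-covers where earlier trials suggest the result will lie, since Protocol 4.1.3 reports 100% acute success throughout.

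**Conclusion.** The concern holds as a gap in wording that can produce a wrong figure; it does not show that the planned estimator is wrong. Followed literally, the rule doubles the estimate in the simplest case, from 3.3% to 6.7%, takes the interval outside its assumptions, and sets the primary safety result against the secondary one. It can only overstate risk, and it changes nothing if no subject has two qualifying events. With 30 subjects and the earlier event rates, the chance that it matters is roughly 1-16%, for assumed second-event shares of 2-20%. It is a minor correction, worth making because it costs almost nothing.

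The vein point is smaller. Protocol 11.3.2 does not fit a per-vein proportion, and a plain exact interval on veins ignores clustering. The practical effect is slight if isolation is near complete. The 116/120 example and the four veins per subject are assumptions.

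**What to change.** **Primary safety.** In Protocol 11.1.1.1.3, 11.2 and 11.3.1 and in SAP 3.2.3 and 4, define incidence as the number of subjects with at least one primary safety event, divided by the ITT subjects classed as ATTEMPT or TREATMENT. Put the exact 95% interval on that proportion. List event counts by component separately, without an interval. The planning table stands as printed once its first column is read as subjects with an event.

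**Vein endpoint.** In Protocol 11.1.2.3 and 11.3.2 and in SAP 3.3, state that the denominator is all pulmonary veins present in the analysed TREATMENT subjects. Then do one of two things:
- give an interval that allows for veins clustered within subject, by a method of the statistician's choice named in the SAP; or
- report the per-vein proportion without an interval and refer to the subject-level exact interval for acute success. Because the vein endpoint is reported for both ITT and mITT while acute success is planned for mITT only, the subject-level figure should come from the matching set.

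**Cost.** One sentence for safety and one or two for the veins in each document, plus a few lines of code. No new data are needed. The only drawback is a somewhat wider per-vein interval if the first option is chosen. SAP 5.5 already provides for an amended plan approved before the analyses are run.

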11.1.1.2.1 Hypothesis

This is an observational real-world study with small sample size; thus, no formal hypothesis is performed in this study.

11.1.1.2.2 Sample Size

There is no formal hypothesis for this study, thus no sample size calculation is performed in this study. The study device has achieved CE mark and accumulated a large amount of clinical data. This trial with 30 PAF subjects will be used to produce data in Chinese population.

11.1.1.2.3 Statistical Methods

Descriptive statistics will be conducted for the effectiveness endpoint events. The number, incidence (amount of events/number of subjects) and its 95% confidence interval (exact methods) will be calculated. The primary effectiveness endpoints will be analyzed for TREATMENT subjects in the mITT set. Explorative statistical analysis might be produced if appropriate, e.g., Bayesian estimation of the study results using FARAPULSE IDE data as the prior.

11.1.2. Secondary Endpoints

11.1.2.1. Secondary Safety Endpoints

The secondary safety endpoint will evaluate the proportion of subjects that free from primary safety events defined in **Section 6** through 7 days after the procedure and free from the following serious procedure-related and/or device-related adverse events at any time through the completion of 12-month follow-up visit, which will be assessed at the time of the twelve-month analysis:

- Atrial esophageal fistula
- Severe PV stenosis
- Persistent phrenic nerve palsy*

**The study will collect information on phrenic nerve palsy observed before the end of the index procedure and, in case of occurrence, will track information for potential recovery during the study visits.*

11.1.2.2. Secondary Effectiveness Endpoint 1

The first secondary effectiveness endpoint will evaluate the chronic success, which is defined as proportion of subjects that free from effectiveness events defined as failure as below at twelve months post-procedure.

Effectiveness events determining a failure are defined as:

- Fail to achieve electrical isolation of all PVs using FARAPULSE Pulsed Filed Ablation system only.
- After the Blanking Period to 12-month after the procedure:

- a) Occurrence of any Detectable AF, AFL* or AT captured by one of the following methods: ≥ 30 seconds in duration recording from 24-hour or longer Holter Monitor or ≥ 10 seconds recording from 12-lead ECG.
- b) Any cardioversion for AF, AFL* or AT.
- c) Use of any Class I or Class III AADs[#] for the treatment of AF, AFL* or AT.
- At any time through 12 months after the procedure:
 - a) Re-ablation for AF, AFL* or AT.
 - b) Use of amiodarone, except intra-procedurally to control an arrhythmia.

#It won't be considered as a failure if the subject has three-month visit happened after 90 days post the procedure, but still in the window (≤ 104 day) with AADs on, and physicians decide to take AADs off after this visit.

**excluding CTI-dependent flutter confirmed by EP study*

11.1.2.3. Secondary Effectiveness Endpoint 2

The second secondary effectiveness endpoint will evaluate the proportion of PVs that achieve electrical isolation by using the FARAPULSE Pulsed Field Ablation system only.

11.1.2.4. Secondary Effectiveness Endpoint 3

The third secondary effectiveness endpoint will evaluate the chronic success when allowing AADs, which is defined as proportion of subjects that free from effectiveness events defined as failure as below at 12 months post-procedure.

Effectiveness events determining a failure are defined as:

- a) Fail to achieve electrical isolation of all PVs using FARAPULSE Pulsed Field Ablation system only.
- b) After the Blanking Period to 12-month after the procedure:
 - Occurrence of any Detectable AF, AFL* or AT captured by one of the following methods: ≥ 30 seconds in duration recording from 24-hour or longer Holter Monitor or ≥ 10 seconds recording from 12-lead ECG.
 - Any cardioversion for AF, AFL* or AT.
- c) At any time through 12 months after the procedure:
 - Re-ablation for AF, AFL* or AT.

**excluding CTI-dependent flutter confirmed by EP study*

